9.5. Definition and reporting of (serious) adverse events

9.5.1. Definition of Adverse Event and Serious Adverse Event

An AE is any untoward medical occurrence in a patient or clinical investigation subject to whom a medicinal product is administered. The occurrence does not have necessarily a causal relationship with the treatment. An AE can therefore be any unfavorable and unintended sign (including an abnormal laboratory finding, for example), any symptom or disease, whether new or exacerbated, temporally associated with the use of a medicinal product, whether or not related to the investigational drug product.

An AE, whether or not considered to be causally related to the investigational drug product, may be:

- The deterioration of a pre-existing chronic disease or aggravation of a symptom or disease that was present at inclusion of the patient in the study.
- A symptom or disease discovered after the start of the study even if it was probably present prior to the patient's inclusion.
- Abnormal laboratory findings when they are considered as clinically significant by the Investigator.

In case a vital sign shows a clinically significant abnormality, an AE should be reported (or the abnormal vital sign should be linked to an already reported AE). A serious AE is an AE that, at any time, fulfils one or more of the following criteria:

- results in death,
- is life threatening (the patient was at risk of death at the time of the event; it does NOT refer to an event which hypothetically might have caused death if it were more severe),
- requires in-patient hospitalisation or prolongation of existing hospitalisation - hospitalisation required by the study will not be considered as an AE,
- results in persistent or significant disability/incapacity (substantial disruption of a person's ability to carry out normal life functions),
- is a congenital anomaly/birth defect,

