- is any important medical event that may not be immediately life threatening or result in death or hospitalisation but, based upon appropriate medical judgment, may endanger the patient or may require intervention to prevent one of the other outcomes listed in the definition above, and should also be reported in the same way as an SAE. Examples of such events are invasive or malignant cancers, intensive treatment in an emergency room or at home for allergic bronchospasm, blood dyscrasias or convulsions that do not result in hospitalisation; or development of drug dependency or drug abuse.

Distinction should be made between serious and severe AEs. Severity is a measure of intensity whereas seriousness is based on the outcome or the action criteria described above, for example, nausea that persists for several hours may be considered as severe, but not as an SAE. On the contrary, a cardiovascular event that causes limited degree of disability may be considered as not severe but would be recorded as an SAE.

- Events initially reported as an AE may become serious. For example, diarrhoea may become debilitating and require hospitalisation or prolongation of hospitalisation and is then reported as an SAE.
- Surgical intervention is not to be considered as a SAE but the medical condition requiring the surgery is to be reported as such.
- If a medical condition known before the start of study treatment requires hospitalisation for planned surgical measures, it should not be considered as an AE. However, the medical condition should be reported in the medical history.
- Occurrence of study drug misuse/abuse, overdose or drug dependency, whether or not associated to an adverse event, must be recorded, reported immediately to the Sponsor.

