9.5.3. Adverse Event recording and reporting

Period of (Serious) Adverse Event Data Collection:

In order to ensure complete safety data collection, recording and reporting, all (S)AEs occurring during the study, i.e. after signature of the Informed Consent, must be recorded, even if no study drug was administered. These include all AEs occurring, recurring, or worsening after the signature of the informed consent. The period of observation for the study is from the screening visit to the end of study visit.

If the Investigator becomes aware, after that period, of any unusual safety information or any safety information that appears to be drug related involving a patient who had participated in the study, even after the patient completes the study, he/she should contact the sponsor to determine how it should be documented and reported.

Recording and Description of (Serious) Adverse Event:

All AEs occurring after signature of the informed consent until the end of study visit will be recorded in the appropriate pages of eCRF, including AEs occurring during the screening period and before the first administration of study drug, other than baseline findings which will be recorded as medical history.

Each individual AE is to be listed as a separate entry on the eCRF AE form. The Investigator will provide information on dates of onset and resolution, seriousness, severity, frequency, action(s) taken with regard to corrective therapy or to the study drug, outcome and relationship to the study drug. The Investigator must report to the Sponsor or its designee all AEs that occur during the study from the time the written informed consent is given until the EOS visit or premature termination, regardless of their relationship to the study drug. Apart from AEs clinically observed by the Investigator, the patient will be given the opportunity to report AEs spontaneously. A general prompt will also be given to detect AEs, e.g. "Did you experience any illness or unusual symptom since your last visit?"

Follow-up of Adverse Events:

All AEs and SAEs assessed as not related to study medication, including clinically significant laboratory tests or physical examination findings, must be followed until the event resolves, the condition stabilizes, the event is otherwise explained, or the final study visit occurs, whichever comes first.

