12.10.1. Adverse events

All AE will be classified using MedDRA including Lowest Level Terms (LLT), Preferred Terms (PT) and System Organ Class (SOC).

TEAEs defined as AEs occurring after the start of the 1st study drug administration will be analysed. Other AEs will only be listed.

The absolute number of TEAEs as well as the number of patients with at least one TEAE will be tabulated by SOC and PT. Patients with SAEs, drug-related AEs will be analysed by SOC and PT.

The duration of the TEAE and the time between the last administration of study drug and the onset of the TEAE will be calculated.

TAAEs will be analysed by patients and infusions.

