4.7.2. Adverse events

All AEs occurring during the study will be classified by PT and SOC using the version 17.1 of the MedDRA.

Seriousness	Serious if one of the follow-ups is serious / Non-serious otherwise
Seriousness criterion	For each of the criteria listed below: Yes if at least one of the follow-ups had Yes for the corresponding criterion / No otherwise 
▪ Results in death▪ Life-threatening▪ In hospitalisation or prolongation of existing hospitalisation▪ Persistent or significant disability / incapacity▪ Congenital anomaly / birth defect▪ Important medical event
Start date time	Start date time of the first follow-up
End date time	End date time of the last follow-up
Ongoing	Yes if last sequence follow-up is ongoing / No otherwise
Did the AE start within 72h after an infusion?	Yes if the first follow-up started within the first 72h after an infusion / No otherwise
Intensity	Maximum (Intensity of follow-ups) Increasing order of importance: Mild / Moderate / Severe
Action taken	Maximum (Action taken of follow-ups) Increasing order of importance: None / Dose changed / Interruption of IMP / Discontinuation of IMP
Corrective medication	Yes if at least one of the follow-ups had a corrective medication / No otherwise
Relationship to study drug	Yes if at least one of the follow-ups had a relationship to study drug assessed as Yes / No otherwise
Outcome	Maximum (Outcome of corresponding follow-ups) Increasing order of importance: Unknown / Recovered without sequela / Recovered with sequelae / Recovering / Not recovered / Fatal

AEs will be classified as Pre-treatment or Treatment-Emergent according to the date of onset:

- Pre-treatment AE defined as an event with a date-time of onset before the first infusion date-time.
- TEAE defined as any event with a date-time of onset on/after the start date-time of the first infusion.

Treatment emergent adverse event flag

The following rules for the derivation of the TEAE status will be used in the order of display:

- If the date-time of the AE onset is known: TEAE = “Yes” if AE onset date-time \geq start date-time of first IMP infusion / “No” otherwise
- If the date-time of the AE onset is not known but the complete date of the AE onset is known:

- TEAE = “Yes” if AE onset date > start date of first IMP infusion

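### Treatment-emergent status rests on first onset alone, so a screening-period AE that becomes serious after I10E, or whose worsening is entered as a follow-up, is left out of the TEAE summaries

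*SAP*

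**What the plan says.** **SAP 4.7.2** makes three choices that act together.

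- Follow-up records of one AE are combined. The combined start is given as "Start date time of the first follow-up". The event is serious "if one of the follow-ups is serious", its intensity is the maximum over the records, and it is related if any record is.
- The split is then made on onset. The pre-treatment class reads "Pre-treatment AE defined as an event with a date-time of onset before the first infusion date-time", and its counterpart reads "TEAE defined as any event with a date-time of onset on/after the start date-time of the first infusion".
- Pre-treatment AEs are listed, not tabulated.

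**Protocol 12.10.1** also defines TEAEs by occurrence after the first administration begins, and adds: "Other AEs will only be listed".

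**Protocol 9.5.1 and 9.5.3** define an AE more widely. An AE may be the "aggravation of a symptom or disease that was present at inclusion of the patient in the study", and protocol 3.1.3 places inclusion at the first study drug administration. On what must be recorded, 9.5.3 says: "These include all AEs occurring, recurring, or worsening after the signature of the informed consent". On seriousness, 9.5.1 says: "Events initially reported as an AE may become serious".

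**SAP 4.10.2**, which declares the safety changes from the protocol, does not mention the point.

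**The concern.** The combined record can describe something that never happened at one time: a pre-infusion start joined to post-infusion severity, seriousness and drug relationship. Because the flag looks only at the start, an event that the drug may have aggravated is treated as if it had run its course before treatment.

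Safety is the secondary objective (protocol 2.2) and TEAEs are a safety endpoint (protocol 3.2.3). With a single arm there is no comparator in which the same rule would remove a similar share of events. Compared with a definition that includes worsening, the omission can only lower the TEAE counts. The pre-treatment listing would meanwhile hold events that carry post-dose severity and a drug relationship.

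**Working it through.** The plan gives no figure to reproduce. The check applies the written rules to an invented case and then sizes one patient.

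**Inputs.** Combination and flag rules: SAP 4.7.2. Screening of at most 4 weeks: protocol 3.1.1. Planned number of patients, 42: protocol 5.1.

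**Step 1: one AE with two records.** Day 0 is the start of the first infusion.

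| Record | Start | Intensity | Serious | Related |
|---|---|---|---|---|
| First | day −10 | mild | no | no |
| Second | day +2 | severe | yes | yes |
| Combined under SAP 4.7.2 | day −10 | severe | yes | yes |

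Flag: is −10 ≥ 0? No. The event is a pre-treatment AE that is severe, serious and related.

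**Step 2: the same course as two separate AEs.** The entry at day −10 is not treatment-emergent. The entry at day +2 is (+2 ≥ 0), and it counts as severe, serious and related. The tables therefore depend on how the site entered the worsening.

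**Step 3: do the other flag rules help?** SAP 4.7.2 has rules for a known date-time, a known date only, and a partial date. None looks at a later record. When the onset date-time is known and precedes the infusion, the answer is always no.

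**Step 4: where the combined event appears.**

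- Left out: the overall TEAE summary and its serious, drug-related and severity rows.
- Kept: the pre-treatment listing and, from its wording, the listing of drug-related AEs.
- Unclear: the SOC and PT tables. They name SAEs and drug-related AEs without a treatment-emergent limit, but the count they display is of TEAEs.
- Undefined: time since the last infusion before onset (SAP 4.7.2 and 5.7.2). No infusion precedes day −10.

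**Step 5: AE definition against TEAE definition.** Protocol 9.5.1 counts aggravation of something present at the first dose as an AE in its own right. It treats becoming serious as a change in an event already reported. Neither TEAE definition has a place for either change when the first record is earlier than the infusion.

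**Step 6: size.** Shift in a patient percentage = k / 42 for k patients whose only event in the category is lost.

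- k = 1: 1/42 = 2.4 points
- k = 2: 2/42 = 4.8 points
- k = 3: 3/42 = 7.1 points

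The values of k are assumptions. The documents give neither the rate of screening AEs nor the share that worsen.

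**The case against.** The strongest reply is that the protocol already prevents the loss. If aggravation after the first dose is itself an AE, and 9.5.3 requires every AE to be entered on its own, a worsening could be opened as a new AE with a post-dose onset and would count. This stands in part. For worsening, the loss arises only when the site enters it as a follow-up. Taking the maximum intensity over follow-ups implies that some changes are recorded that way, but neither document says which entry is required; protocol 11.1 refers to separate eCRF guidelines. For an event that becomes serious the reply is weaker, because protocol 9.5.1 describes one event changing status.

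Four stronger readings are tempting, and the documents do not support them.

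- **That the SAP departs from the protocol.** Protocol 12.10.1 also omits worsening. The gap lies between the AE definition and the TEAE definition in both documents.
- **That the events vanish.** They remain in listings, and the SOC and PT tables are ambiguous rather than clearly closed to them.
- **That the plan leans generally towards undercounting.** When the timing of an onset is uncertain, the rules of SAP 4.7.2 mostly lean towards inclusion and the last default is treatment-emergent.
- **That many events are affected.** Screening-test abnormalities go to medical history, so their later worsening would be a new AE with a post-dose onset. CIDP worsening is not an AE (protocol 9.5.2). SAP 2.4 notes that screening was at most 15 days under one protocol version.

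**Conclusion.** The point holds as a defect of definition with small reach. As written, an AE that starts in screening and becomes serious after the first infusion is not treatment-emergent. The same is true of one whose worsening is entered as a follow-up, and both leave the TEAE, serious-TEAE, drug-related-TEAE and severity summaries.

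The direction is known: counts can only be too low relative to a definition that includes worsening. The size is not. It rests on events that begin within at most 4 weeks, are ongoing at dosing and then change. One patient is worth 2.4 points only if that patient has no other event in the category over the study. That condition is harder to meet for any TEAE than for the serious or severe rows, where a single event matters most.

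The sample size, the primary test and the efficacy results are unaffected. The change is worth making because the follow-up records it needs are already used in the SAP's derivations.

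**What to change.** - **SAP 4.7.2, definition.** Define a TEAE as an event with onset at or after the start of the first infusion, or an event with earlier onset that increases in intensity or becomes serious at or after that time.
- **SAP 4.7.2 and 5.7.2, dating.** For the second kind, use the first worsened or serious follow-up record as the onset for the TEAE flag and for time since infusion.
- **Pre-treatment listing.** Keep only screening events that did not change in this way.
- **Protocol 12.10.1 or SAP 4.10.2.** Align the protocol definition, or declare the change.
- **Entry rule.** State whether a worsening opens a new AE or a follow-up, so that the same course is not counted twice or missed.

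Two additions should be avoided. A first assessment of relatedness after dosing should not make an unchanged event treatment-emergent, since nothing has emerged. TAAE status should stay with the eCRF item Schedule, from which SAP 4.7.2 derives it.

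The cost is a sentence or two of text and minor programming on follow-up records that the SAP already uses. The reported TEAE rate may rise slightly.

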- TEAE = “Yes” if AE onset date = start date of first IMP infusion and investigator’s assessment of the time of onset ≠ “Before infusion”
- TEAE = “No” otherwise
- If the date of AE onset is a partial date and the investigator’s assessment of the time of onset is not missing: TEAE = “Yes” if investigator’s assessment of the time of onset “During infusion”, “≤72h” or “>72h”
- If the date of AE onset is a partial date and the investigator’s assessment of the time of onset is missing:
 - TEAE = “Yes” if last possible date in the period defined by the partial date ≥ start date of first IMP infusion / “No” if the last possible date in the period defined by the partial date < start date of first IMP infusion
- TEAE = “Yes” otherwise

Temporally associated adverse events (TAAEs)

TAAE will be defined according to the item “Schedule” collected in the eCRF. They will include all adverse events with Schedule “During infusion”, “Within 72 hours after the end of the infusion”. If Schedule is missing then the event will be classified as TEAE by default.

Other significant AEs

Other Significant AEs are based on the definition of relevant AESIs (Adverse Events of Special Interest) for I10E. They are defined as standardized MedDRA queries (SMQs) of interest on the narrow scope, these are:

- Anaphylactic reaction (SMQ) [20000021] narrow scope
- Anaphylactic/anaphylactoid shock conditions (SMQ) [20000071] narrow scope
- Noninfectious meningitis (SMQ) [20000134] narrow scope
- Embolic and thrombotic events, vessel type unspecified and mixed arterial and venous (SMQ) [20000083] narrow scope
- Acute renal failure (SMQ) [20000003] narrow scope
- Hemolytic disorders (SMQ) [20000019] narrow scope
- Eosinophilic pneumonia (SMQ) [20000157] narrow scope
- Interstitial lung disease (SMQ) [20000042] narrow scope

Pre-treatment Adverse Events

Pre-treatment AEs will be listed for all enrolled patients.

Summary of treatment Emergent Adverse Events (TEAE)

A summary of the total number of TEAEs, and number and percentage of patients with at least one TEAE will be presented. This summary will include the number and percentage of patients having at least one TEAE as well as the absolute number of TEAEs in each AE category:

- TEAEs
- Serious TEAEs by seriousness criterion

- Drug-related TEAEs
- TAAEs
- TEAEs by severity (Mild / Moderate / Severe)

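### SAP 4.7.2 gives no outcome for a partial-date adverse event timed 'Before infusion'; it defaults to treatment-emergent, which is wrong when the whole date window precedes the first infusion

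*SAP*

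**What the plan says.** SAP 4.7.2 defines the two classes of event by onset relative to the first infusion:

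- The first class covers what happens before treatment: "Pre-treatment AE defined as an event with a date-time of onset before the first infusion date-time".
- The second class covers everything later, and its wording is: "TEAE defined as any event with a date-time of onset on/after the start date-time of the first infusion".

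It then sets out how the flag is derived: "The following rules for the derivation of the TEAE status will be used in the order of display". The SAP does not number the rules; I number them here in the order shown.

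1. **Onset date-time known.** 'Yes' if on or after the start of the first infusion, otherwise 'No'.
2. **Complete date, no time.** 'Yes' if the date is after the first infusion date, or "if AE onset date = start date of first IMP infusion and investigator’s assessment of the time of onset ≠ “Before infusion"; otherwise 'No'.
3. **Partial date, timing recorded.** This rule applies when the onset date is incomplete but the recorded "assessment of the time of onset is not missing". The flag is then 'Yes' "if investigator’s assessment of the time of onset “During infusion”, “≤72h” or “>72h". No other outcome is given.
4. **Partial date, timing missing.** 'Yes' if the last possible date is on or after the first infusion date, 'No' if it is earlier.
5. **Closing line.** "TEAE = “Yes” otherwise".

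**The concern.** Rules 1, 2 and 4 each state when the flag is 'No'. Rule 3 does not, although rule 2 shows that 'Before infusion' is an answer the investigator can give.

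Such events can occur. Protocol 9.5.3 records adverse events from consent, and screening may last up to 4 weeks (protocol 3.1.1). The patient receives a diary for out-of-hospital events at screening (protocol 8.2.1), and SAP 3.2 expects some diary onset dates to be missing or incomplete.

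A misflagged event would enter the treatment-emergent tables and leave the pre-treatment listing. Protocol 12.10.1 restricts the analysis to events after the start of the first administration and has all others listed only.

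**Working it through.** The plan gives no figure to reproduce. The check is to run the rules in order.

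**Step 1. Trace one event: partial date, timing 'Before infusion'.**

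- Rule 1 does not apply, because there is no date-time.
- Rule 2 does not apply, because there is no complete date.
- Rule 3 meets its condition but assigns no value.
- Rule 4 does not apply, because the timing is present.
- Rule 5 assigns 'Yes'.

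**Step 2. Enumerate the partial-date cases.** There are five possible timings and two window positions (last possible date before the first infusion date, or on/after it), so 5 × 2 = 10 cases.

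| Timing recorded | Window ends before first infusion | Window reaches or passes first infusion |
|---|---|---|
| Before infusion | Yes (by default) | Yes (by default) |
| During infusion | Yes | Yes |
| ≤72h | Yes | Yes |
| >72h | Yes | Yes |
| Missing | **No** | Yes |

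Two of the 10 cases reach the closing line, both with 'Before infusion'.

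**Step 3. Compare the first and last rows of the left column.** Suppose the first infusion is on 5 March and the onset is recorded only as February of that year. The last possible date is before 5 March.

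- Timing missing: rule 4 gives 'No'.
- Timing 'Before infusion': rule 5 gives 'Yes'.

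Confirming that onset came before infusion turns the right answer into the wrong one. The result also contradicts the SAP's definition of a pre-treatment event, and it departs from rule 2, which gives 'No' for a complete date on the first infusion day with the same timing.

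**Step 4. Look at the right column.** Keep the first infusion on 5 March and put the second course three weeks later, on 26 March. An onset recorded only as March could be a screening event from 1 to 5 March, or one that arose after the first course and before the second. Rule 2 ties 'Before infusion' to the first infusion through the date; rule 3 has no such tie. The documents cannot settle this case.

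**Step 5. Size.** Protocol 12.3 plans 42 patients.

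- Event counts: +1 per affected event.
- Patient-level row, overall column: at most 1/42 = 2.4 percentage points, and 0 if the patient already counts in that row.
- Subgroup columns have smaller denominators. With an assumed 14 patients (42/3), the ceiling is 1/14 = 7.1 points.

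The clear-cut case is also narrow. If only the day is missing, the window is a calendar month. It ends before the first infusion only when onset falls in an earlier month, so the screening period must cross a month end.

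**The case against.** **'Before infusion' may not mean before the first infusion.** The other timings are relative to an infusion in general, and each patient is planned to have eight courses. If an investigator used the answer for an event before a later course, 'Yes' is correct. This stands. A reader might infer that every partial-date event timed 'Before infusion' is known to be pre-treatment and so miscounted. The documents do not support that; it is certain only when the window ends before the first infusion. For the same reason, a blanket 'No' for 'Before infusion', or a 'No' whenever the window merely starts by the first infusion date, could remove genuine treatment-emergent events. That is the less safe direction.

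**The closing line may belong under rule 4.** List indentation is unreliable in the text available. Rule 4 already states both of its outcomes, so a general default is the more natural reading, although a nested line could serve a wholly missing date. If it is nested, the case has no assigned value. The gap in rule 3 remains either way.

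**Defaulting to 'Yes' is cautious.** Rule 4 does so whenever onset after the first infusion is possible, and the same section defaults to treatment-emergent when the eCRF timing item used for temporally associated events is missing. That is sound for uncertain timing. It does not justify 'Yes' when date and timing both place onset before treatment.

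**Little is hidden in practice.** Listings show the values as recorded (SAP 3.2) and cover all data (SAP 5.1). The diary asks for dates and times, queries are raised on inconsistencies (protocol 11.2), and a data review precedes lock (protocol 12.2). This stands as a reason for low priority. It does not correct the tables.

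**Conclusion.** The point holds in a limited form. Rule 3 is incomplete. On the natural reading it sends partial-date events timed 'Before infusion' to 'Yes', and this is wrong when the whole window precedes the first infusion. Where the window includes the first infusion date, the result is undetermined until the SAP says which infusion the item refers to. Where the window lies wholly after that date, 'Yes' is right.

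The clear error can only inflate the treatment-emergent counts. The 2.4-point ceiling is per affected event and assumes 42 treated patients. The documents do not say how many such events there are, and the narrow conditions suggest few. Only the safety tables and the pre-treatment listing are involved. Nothing here supports a wider inference that the safety analysis is unsound, and the efficacy analyses do not use this flag.

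**What to change.** Complete rule 3 for a timing of 'Before infusion':

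- 'No' if the last possible date in the partial period is before the first infusion date.
- 'Yes' if the first possible date in the period is after the first infusion date.
- If the period includes the first infusion date, 'No' only where the eCRF definition or a query confirms that the item refers to the first infusion; otherwise keep 'Yes'.

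State in the SAP which infusion the timing item refers to, and place the closing default explicitly at the level of the rules.

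The cost is a few lines of SAP text, the matching program code, and a query for each event whose window includes the first infusion date. No new data collection is needed.

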EFFICACY ENDPOINTS	
Primary efficacy endpoint: Responder rate at EOS visit.
 
Responders are defined as patients with a decrease ≥ 1 point in the adjusted INCAT disability score between baseline and the EOS visit.
 
Secondary efficacy endpoints:
 
 – Responder rate at 12 weeks. – Time to response. – Percentage of patients at 12 weeks and EOS visit with no change in CIDP treatment. – Changes from baseline to 12 weeks and EOS visit in the following scores: 
 * Adjusted INCAT disability score; * Grip strength with the Martin vigorimeter in both hands; * Rasch-built Overall Disability Scale (R-ODS); * Patient and Investigator Clinical Global Impression (CGI); * Medical Research Council (MRC) 12 muscles sum score (0 to 5) and Rasch-modified MRC (0 to 3).
SAFETY ENDPOINTS	
Treatment-emergent adverse events (TEAEs), including serious adverse events (SAEs), from first study drug administration to the EOS visit.
 
Temporally-associated Adverse Events (TAAEs), defined as AEs occurring during study drug administration or within 72 hours post-administration (end of infusion).
 
Clinically significant changes from baseline in vital signs and laboratory tests.

STUDY N° / ACRONYM	I10E-1302 / PRISM

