2.5.3. Safety criteria

The safety criteria include:

- Treatment emergent adverse events (TEAEs)
- Serious adverse events (SAEs)
- Temporarily associated adverse events (TAAEs), i.e., AEs that begin during an infusion or within 72 hours after an infusion
- Clinically significant changes from baseline in vital signs
- Clinically significant changes from baseline in laboratory parameters

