3.2. Handling of Missing Data and Outliers

Regarding the primary criterion, a patient will be also considered as a non-responder if the patient is withdrawn due to lack of efficacy of the treatment (insufficient response to the investigational medicinal product [IMP]). In all other cases, if the INCAT score at EOS visit is missing, then the Last Observation Carried Forward (LOCF) approach will be applied and the last available adjusted INCAT disability score will replace the missing value at EOS visit.

The LOCF approach will also be used to handle the missing data of the secondary endpoint for adjusted INCAT and response at week 12 only.

When AEs are documented in the diary, dates of AE onset may be missing and as a result, TAAE cannot be defined. For AEs with a missing or incomplete start date, the response to the question “Did the AE start within 72 hours of an infusion” will be used for determining if the AE is temporally related to the infusion.

Partial dates of first symptoms and partial dates of diagnosis will be imputed by 15 if only the day is unknown and by 1st July if day and month are unknown. No imputation will be done if the year is unknown.

For the calculation of duration of AEs, partial start and end dates will be imputed with the first and last possible date within the period defined by the partial date, respectively. In general, no

calculation of duration will be made if either the start date or stop date is missing, i.e., cannot be imputed using pre-determined rules. No other general rules for the replacement of missing data are planned.

Data listings will always show the original CRF reported values and not the imputed values.

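### When the Schedule item is missing, SAP 4.7.2 ignores the recorded onset time in classifying temporally associated events, although they are defined by onset time

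*SAP*

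**What the plan says.** **Definition.** The protocol Synopsis (Safety endpoints) describes TAAEs as "defined as AEs occurring during study drug administration or within 72 hours post-administration (end of infusion"). SAP 2.5.3 agrees: "AEs that begin during an infusion or within 72 hours after an infusion". Both rest on time of onset.

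**Operational rule.** SAP 4.7.2 changes the basis: "TAAE will be defined according to the item “Schedule” collected in the eCRF". Two Schedule values qualify, one for onset during the infusion and one for onset in the 72 hours after its end. The paragraph closes with "If Schedule is missing then the event will be classified as TEAE by default".

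**Missing-data rule.** SAP 3.2 starts from onset date. It notes that for diary events "dates of AE onset may be missing and as a result, TAAE cannot be defined", and then: "For AEs with a missing or incomplete start date, the response to the question" on whether the event began within 72 hours of an infusion decides the matter.

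**Data held.** The adverse event table in SAP 4.7.2 carries a start date-time ("Start date time of the first follow-up") and a separate yes/no variable on the 72-hour window. Protocol 6.1.3.3 has the date and time of administration entered in the eCRF. Protocol 8.2.1 has patients note start and end dates and times in the diary.

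SAP 4.10.2, which lists safety changes from the protocol, does not mention the Schedule-based rule.

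**The concern.** TAAEs are a named safety endpoint. Protocol 12.10.1 has them analysed by patients and by infusions, and SAP 4.7.2 gives them their own summary table and a table by system organ class and preferred term. Protocol 10.2 schedules a telephone call after each course so that none is missed. A rule that turns on whether one eCRF field is filled, when the times that define the endpoint are already in the database, can misclassify an event whose true status is known.

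The trial has no control arm in which the same misclassification would also occur. The planned size is 42 patients, so one patient is 1/42 = 2.4% of the denominator. One misclassified event can therefore move a preferred-term row by up to about 2.4 percentage points.

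**Working it through.** The plan gives no figure to reproduce here, so the check is to trace the written rules. *Literal* means that an event with missing Schedule becomes a TEAE and, having neither qualifying value, is not a TAAE. *Slip* means that TAAE was intended in that sentence. Schedule is missing in every row, and the onset times are illustrative.

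| Case | Onset-based definition (Synopsis, SAP 2.5.3) | SAP 3.2 | SAP 4.7.2, literal | SAP 4.7.2, slip |
|---|---|---|---|---|
| A. Onset 10 hours after infusion end | TAAE | TAAE (implied, date known) | Not TAAE | TAAE |
| B. Onset 10 days (240 hours) after infusion end, no later infusion yet | Not TAAE | Not TAAE (implied, date known) | Not TAAE | TAAE |
| C. Start date missing, 72-hour question answered yes | Cannot be placed | TAAE | Not TAAE | TAAE |
| D. Start date missing, 72-hour question answered no | Cannot be placed | Not TAAE | Not TAAE | TAAE |

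1. **Literal reading.** Case A is wrong. The event is already a TEAE under the first of the ordered TEAE rules in SAP 4.7.2, which compares onset date-time with the start of the first infusion. The default therefore adds nothing, and the only effect is the loss of TAAE status. Errors against the definition can only lower the TAAE count.

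2. **Slip reading.** Case A comes out right, but case B is wrong: 240 hours exceeds 72, yet the event is counted. Errors against the definition can only raise the TAAE count.

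3. **Against SAP 3.2.** The literal reading also disagrees in case C and the slip reading in case D. Both cases assume that Schedule and the 72-hour question are separate eCRF items, which the documents do not settle. SAP 3.2 covers date missing with the question answered. It states no rule for Schedule missing with onset known, which is the situation in A and B.

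4. **Side effect.** Read literally and without qualification, the default would also label an event that began before the first infusion as a TEAE. The ordered TEAE rules in the same section return No for it.

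5. **Size.** Let a be the number of events with missing Schedule and onset inside the window, and b the number with missing Schedule and onset outside it. The literal reading loses a TAAEs, and the slip reading adds b. Neither a nor b can be obtained from the documents. Assuming a percentage of missing Schedule would only return that percentage as the loss, so no range is informative beyond the lower end: zero if the item is always completed.

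**The case against.** The strongest reply is that exclusion is inferred. The sentence says that an event becomes a TEAE, not that it ceases to be a TAAE, and the two are not alternatives, since the SAP's TEAE summary lists TAAEs as one of its categories. Because a TEAE default is redundant for any event after the first infusion, and the sentence stands under the TAAE heading, a typing error is plausible. SAP 3.2 and 2.5.3 also suggest that the authors had onset in mind. This stands in part. It rules out saying that such events are certainly dropped, but it does not rescue the rule, because the slip reading also ignores onset and produces case B.

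Second, the eCRF is not available. Schedule, the 72-hour question and the investigator's assessment of time of onset may be one item or several, and Schedule may be mandatory. Diary checks, telephone calls, queries and the review before database lock (protocol 8.2.1, 10.2 and 11.2) should keep missing entries few. This stands, and it limits the expected size.

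Third, the tables are descriptive. On the literal reading an affected event stays in the TEAE tables. Drug-related and serious events are also listed with time since the last administration, and SAP 5.1 lists all data. This stands too.

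A reader might go further and infer that the SAP systematically understates infusion-related events, or that the default departs from accepted safety practice. The documents support neither. The direction of error depends on which reading is right, the number of events may be zero, and no standard for such defaults is set out in the documents.

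**Conclusion.** The point holds as a defect in a stated rule. With Schedule missing, SAP 4.7.2 decides TAAE status without the onset time that defines the endpoint, and it conflicts with SAP 3.2. Read literally, the rule can only undercount TAAEs; if TEAE is a slip for TAAE, it can only overcount them. The documents do not settle which was meant.

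The consequence is confined to descriptive safety tables and to events with a missing Schedule entry. Its size is unknown and may be nil. It does not touch the primary analysis or, on the literal reading, the TEAE totals for events after the first infusion. The correction is worth making because it is cheap and the data it needs are already collected, not because a material distortion has been shown. The conclusion assumes that 4.7.2 would be programmed as written, with no further derivation outside the SAP.

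**What to change.** Confirm whether TEAE or TAAE is meant in the closing sentence of the TAAE paragraph, and replace that sentence with an ordered rule that 3.2 also refers to. When Schedule is missing:

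1. Derive TAAE from the event's onset date-time against infusion start and end: yes if onset falls from the start of an infusion to 72 hours after its end, no otherwise.
2. If onset cannot be placed, use the answer to the 72-hour question. A recorded No stands and is not overridden by step 3.
3. If that answer is also missing, count the event as a TAAE. This matches the SAP's own final TEAE rule, which resolves an undetermined event to Yes.
4. Report how many events were classified at each step.

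The new text should leave TEAE status to the ordered TEAE rules, which removes the side effect for events before the first infusion. If the Schedule-based definition is kept as the main rule, record it in SAP 4.10.2 as a change from the protocol.

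The cost is a few sentences and a short derivation from variables already held. Compared with the literal reading, the TAAE count may be slightly higher, and step 3 may include a few events that did not begin in the window; the count in step 4 makes that visible.
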